E-mail: [contact]

[contact]

Abbreviation

COPD	Chronic obstructive pulmonary disease
SpO ₂	Arterial oxygen saturation measured by pulse oximetry
ICU	Intensive care unit
LOS	Length of Stay

1. Introduction

1.1 Background and rationale

Trauma is one of the leading causes of death and disability on a global scale.¹ Advanced Trauma Life Support guidelines state serious concern with the appearance of hypoxemia after trauma, and consequently recommend that supplemental oxygen should be provided for all severely injured trauma patients to avoid hypoxemia in the initial phase.² Oxygen is a vital part of human physiology and must be delivered to all metabolically active cells in the body.³ When patients receive supplemental oxygen, a series of autoregulatory mechanisms happen to ensure optimal oxygen levels and prevent hypoxemia and hyperoxemia⁴ which can have different harmful effects.⁵ The lack of oxygen resulting in hypoxemia can potentially be a reversible cause of poor outcomes and in worst case death, hence supplemental oxygen is recommended for trauma patients, although the evidence is sparse.⁶

In other high-risk patient groups, such as surgical and chronic obstructive pulmonary disease (COPD) patients, Loft et al. monitored arterial oxygen saturation (SpO₂) continuously and found that cumulative duration of desaturations with SpO₂ < 85% was significantly associated with myocardial injury after both surgery and exacerbation of COPD.⁷ In stroke patients, Rowat et al. found a higher mortality in patients that experienced hypoxemia, but after adjusting for National Institute of Health Stroke Scale and age, this association was not significant. In the study, hypoxemia was found at all stages during admission.⁸ Using continuous monitoring for 48 hours Sun et al. found that hypoxemia was common and prolonged in patients recovering from noncardiac surgery. Furthermore, this study showed that 90% of hypoxemic episodes SpO₂ < 90% for at least one hour went undetected by standard spot checks, which were typically conducted at intervals of 4-6 hours.⁹

Trauma patients can also be characterized as high-risk patients due to their high mortality.¹⁰ The incidence of prehospital hypoxemia in traumatic brain injury patients has been studied, Stassen et al. found a prevalence of 37.9%,¹¹ and Chi et al. further discovered that prehospital hypoxemia was associated with higher mortality.¹² Evidence about the incidence of hypoxemia in trauma patients after admission to a hospital is not well established. There is reason to suspect that trauma patients can experience episodes of hypoxemia after admission and that the incidence of hypoxemia may differ between day and night as shown in several other patient populations.^{13,14,15} Potential incidences of severe hypoxemia, from patients being admitted to a trauma centre to subsequent care in a ward, should be avoided, since severe hypoxemia is associated with harmful effects.^{7,8} Hypoxemia can be detected and potentially corrected with more advanced measuring equipment.⁹ It is relevant to conduct a study with the purpose of determining the occurrence and distribution over the first 24 hours after hospital admission of hypoxemia by continuous SpO₂ monitoring in trauma patients, since this could potentially have important clinical implications and be useful in improving patient outcomes.

1.2 Study objectives and hypothesis

The aim of this study is to examine the occurrence and duration of episodes of hypoxemia in trauma patients in the first 24 hours after trauma and to compare their incidences during the day (08.00-19.59) and night (20.00-07.59).

We hypothesize that hypoxemic episodes will be more frequent during the night than during the day.

1.3 Study design

This study is a prospective, observational study. The protocol is structured according to the 2013 SPIRIT statement.

2. Methods

2.1 Study setting

This study is a single centre study of trauma patients at Rigshospitalet, Denmark. Rigshospitalet holds the only major trauma centre in the eastern part of Denmark, and every year around 1000 trauma patients are treated here.¹⁶ Patients are admitted from the Capital Region of Denmark with around 1.9 million inhabitants and the Region of Zealand with around 850.000 inhabitants.¹⁷

In the prehospital phase, the initial assessment of trauma patients will often be conducted by a prehospital physician specialized in anesthesiology/critical emergency medicine in Denmark. If patients are to be admitted to the trauma centre at Rigshospitalet, they are usually required to fulfil criteria based on either mechanism of injury or anatomical criteria.¹⁸ A primary, secondary and tertiary triage system is used to optimize patient treatment and ensure continuous monitoring of the patient. The primary triage occurs at the scene of injury. It is intended to assess the patient, identify life-threatening injuries and initiate appropriate interventions in accordance with the ABCDE-principals¹⁹. The secondary triage occurs at the trauma centre at a hospital, where there is more staffing and equipment available. Once at the trauma centre, a team consisting of a wide variety of medical professionals will meet the patient. Often in blunt trauma, patients will get an initial assessment and management followed by a full trauma CT scan depending on the severity and the nature of the patients' injuries. Depending on the findings in the clinical assessment and scan the patient will be admitted for further treatment either at a general ward, where surveillance is less thorough, intensive care unit (ICU) or alternatively directly to the operating room as a part of the tertiary triage.^{2,18}

The patients in this study will be included in the trauma bay at Rigshospitalet.

2.2 Participants

All patients with trauma team activation in the trauma bay at Rigshospitalet, including both direct transport and secondary transfers, will be screened for potential inclusion in the study. Patients will be included if they comply with the following eligibility criteria:

2.3 Inclusion criteria

[figure not shown]
- Patients aged ≥ 18 years
- Blunt or penetrating mechanism of trauma
- Trauma team activation
- Admission to a ward/ICU from trauma centre

2.4 Exclusion criteria

- Patients with a suspicion of carbon monoxide intoxication
- No applicable finger or toe for sensor attachment
- Trauma team activation was cancelled
- No available pulse oximeter at admission

The expected process of patient inclusion and data collection is demonstrated in figure 1.

Figure 1: Flowchart describing patient inclusion and data collection process

2.5 Outcomes

[figure not shown]
Primary outcome

- The occurrence and daily distribution of clinically relevant hypoxemic episodes defined as $\text{SpO}_2 < 90\%$ for > 5 minutes, within the first 24 hours after trauma

Secondary outcomes

- The occurrence of clinically relevant hypoxemic episodes $\text{SpO}_2 < 90\%$ > 5 minutes in different departments including trauma centre, ICU, general ward, operating theatre and recovery room.
- The occurrence of prolonged hypoxemic episodes $\text{SpO}_2 < 90\%$ for > 30 minutes per episode
- Cumulated time of hypoxaemia $\text{SpO}_2 < 90\%$

2.6 Participant timeline

2.7 Sample size

We estimate that 5% of patients during the day and 20% of patients during the night will experience hypoxemia defined as $\text{SpO}_2 < 90\%$ for > 5 minutes. A sample size calculation with an alpha of 5% and a power of 80% estimates a need of 150 study participants. Based on previous experience with continuous pulse oximetry it is expected that 10% will be excluded due to unsuccessful data collection. Therefore, the aim is to include 165 patients.

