2.9 Data collection methods

Continuous pulse oximetry will be used to measure SpO_2 . SpO_2 , heart rate, pulse amplitude and alarm status will be measured every second during a 24-hour period on all study participants.

The Nellcor™ Portable SpO_2 Patient Monitoring System, PM10N (Medtronic, [name]) is used as monitoring device. The Covidien Nellcor FLEXMAX or a similar probe will be placed on the patients' index finger, alternatively another finger or toe. If there are no available extremities the patient will be excluded from the study.

If a patient has a peripheral venous catheter or a blood pressure cuff, the probe is placed on the other arm. The probe cable will be fastened with adhesive band across the back of the patient's hand, as an attempt to prevent untimely probe removal. The monitoring device will be placed in a telemetry bag with a soft fabric string which can be placed in the bed or around the patient's neck if awake. The data will be transferred and stored locally on a secure drive.

Since the study is observational, and we would like to identify episodes of hypoxemia that would go undetected under standard care, the alarm system on our monitoring device will be set restrictive. Alarm if $\text{SpO}_2 < 80\%$ or the heart rate is < 40 beats per minute or > 140 beats pr. minute.

Data collection will continue for up to 24 hours. If there is an untimely removal of the probe, the device will switch off, and data collection will stop at this point, unless the device is turned on again. After 24 hours of measurement, an investigator will collect the device and transfer the data by USB cable to a computer for secure storage and further analysis.

The following data will be obtained by accessing the study participants' medical records.

- Patient characteristics including name, unique patient identifier (civil registration number “CPR nummer”), age, sex, height and weight
- Pre-hospital circumstances including vital signs, Glasgow Coma Score (GCS), mechanism of injury, variables regarding airway management and oxygen treatment, use of sedatives and opioids, transportation mode to the trauma centre
- Vital signs at trauma centre arrival
- Clinical parameters during admission including vital signs, variables regarding airway management and oxygen treatment and use of sedatives and opioids

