2.11 Statistics

To account for artefacts during the measurement period the method described by Haahr-Raunkjaer et al. is used. It is stated that artefacts are defined as SpO₂ values after a change in SpO₂ of more than 4% per second.²¹

Data with assumptions of normal distribution will be described with means and standard deviations, categorical data will be reported with numbers and percentages.

Data with assumption of being non-normally distributed will be reported with medians with interquartile ranges.

The student's t-test will be used for parametric data to compare the two study groups.

The Mann-Whitney-U-test will be used for non-parametric data to compare the two groups (day vs night).

A Kruskal-Wallis test will be used for non-parametric data when comparing the different hospital departments.

The modified Wald method will be used to determine the 95% confidence intervals.

A p-value of <0.05 will be considered statistically significant.

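### The 80% power in section 2.7 matches two independent groups of 75, not a design in which each patient normally contributes to both day and night; the mismatch is conservative

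*Combined protocol and SAP*

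**What the plan says.** - Section 2.7 sets the rates: "We estimate that 5% of patients during the day and 20% of patients during the night will experience hypoxemia". It continues: "A sample size calculation with an alpha of 5% and a power of 80% estimates a need of 150 study participants". It gives no test, sidedness, group sizes or within-patient correlation. It then allows for failed recordings ("it is expected that 10% will be excluded due to unsuccessful data collection") and sets the target at 165.
- Section 2.9 says that the oximeter signals "will be measured every second during a 24-hour period on all study participants". The same section says that collection lasts up to 24 hours and stops if the probe comes off, unless the device is switched on again.
- Section 1.2 divides the clock into a 12-hour day (08.00-19.59) and a 12-hour night (20.00-07.59).
- Section 2.11 treats day and night as two groups. It names the t-test and the Mann-Whitney U test, both unpaired, and no paired test. It adds: "A p-value of <0.05 will be considered statistically significant".

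**The concern.** A 24-hour recording contains one full day's worth and one full night's worth of clock time. A patient with complete data therefore supplies both a day status and a night status. With 150 such patients there are 150 day and 150 night observations on the same people, not 75 of each on different people. If 150 came from a two-group formula, the 80% describes a study that is not being done.

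What is at stake is how the result is read. The power statement and the smallest detectable difference that it implies are the yardstick for a null finding, and here the yardstick is wrong. The plan also gives no assumption about how day and night status go together within a patient, which determines the power of a paired comparison.

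**Working it through.** **Inputs.** Day rate 0.05, night rate 0.20, alpha 5%, power 80%, N = 150 (all section 2.7). Two-sided testing is assumed, since the plan does not say. The proportion hypoxemic in both periods, p11, is not given. Because only 5% are hypoxemic by day, p11 can lie only between 0 and 0.05; independence is 0.05 × 0.20 = 0.01.

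**1. Reproducing 150 (independent groups, pooled variance).** The mean rate is 0.125.

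n per group = [1.96√(2 × 0.125 × 0.875) + 0.8416√(0.05 × 0.95 + 0.20 × 0.80)]² / 0.15²
= [1.96√0.21875 + 0.8416√0.2075]² / 0.0225
= (0.9167 + 0.3834)² / 0.0225 = 75.1.

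Power at 75 per group: Φ[(0.15√75 − 0.9167)/0.4555] = Φ(0.839) = 79.9%. So 2 × 75 = 150 with 80% power is reproduced (strict rounding up would give 76 per group, 152 in total). Other two-group versions fit less well: two-sided unpooled 146, two-sided arcsine 140, two-sided with continuity correction 176, one-sided 120, one-sided with continuity correction 144.

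**2. Paired calculation at 80% power (McNemar, normal approximation).** With s = 0.25 − 2·p11 (total discordance) and d = 0.15:

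n = [1.96√s + 0.8416√(s − d²)]² / d²

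| Overlap p11 | s | n, approximation | n, exact test |
|---|---|---|---|
| 0 (none) | 0.25 | 85 | 92 |
| 0.01 (independence) | 0.23 | 78 | 83 |
| 0.05 (maximum) | 0.15 | 50 | 52 |

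No feasible overlap gives 150.

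**3. Power with 150 complete pairs, 5% vs 20%.** Approximation: Φ[(d√n − 1.96√s)/√(s − d²)]. Under independence this is Φ[(1.8371 − 0.9400)/0.4555] = Φ(1.97) = 97.6%.

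| Overlap p11 | Approximation | Exact |
|---|---|---|
| 0 | 96.4% | 96.0% |
| 0.01 | 97.6% | 97.5% |
| 0.05 | 99.9% | >99.9% |

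**4. Fewer complete pairs.** With 100 pairs, exact power is 83.7% with no overlap and 87.6% under independence.

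**5. Detectable difference.** With 150 pairs, 80% power and a 5% day rate, the approximation gives a night rate of 15.3% (no overlap), 14.7% (independence) or 12.9% (phi 0.3). The exact test needs slightly more: at 5% vs 14.7% under independence its power is 76.2%, and at 5% vs 15% it is 78.4%. Roughly 13% to 16% is a fair range from no overlap to phi 0.3; greater overlap would lower it further.

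**6. Does the unpaired test in section 2.11 rescue the 80%?** Taken at face value, 150 day against 150 night observations give Φ[(0.15√150 − 0.9167)/0.4555] = Φ(2.02) = 97.8%. The 80% fails on the count of observations alone.

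**The case against.** **The formula is not stated.** True. That it is a two-group calculation is an inference. It is a strong one, because the two-group formula returns the stated power almost exactly and no paired calculation comes near 150.

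**Section 2.7 agrees with section 2.11, which also treats day and night as independent.** This stands in part: the two sections share one assumption, and correcting only section 2.7 would leave the power statement and the named tests in conflict. It does not save the 80%, as step 6 shows.

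**Patients might be grouped by admission time.** The amendment in section 3.9 plans to compare the characteristics of patients included in day and night time. It defines no such groups for the primary outcome, which sections 1.2 and 2.5 describe by when episodes occur.

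**There may not be 150 pairs.** This stands. Recordings can end early, and the 10% allowance is for failed collection, not for recordings that miss one period. On the plan's own rates, power stays above 80% with 100 complete pairs.

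**The error does no harm to the size of the study.** This also stands, and it limits the point. A reader might infer from a wrong power statement that the study is too small; the figures show the opposite. A reader might also infer that the ethics committee was given a faulty case for enrolling patients without prior consent. The documents do not show what was put to the committee beyond this paragraph, so they do not support that inference.

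**Conclusion.** The point holds as a mismatch between the sample size method and the design; the arithmetic itself reproduces. The stated 80% should read at least 96% for 5% vs 20% with 150 complete pairs (exact McNemar, two-sided 5%, whole feasible range of overlap), and about 97.5% under independence. At 80% power, about half as many complete pairs would be enough, or a smaller difference could be detected.

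This rests on the plan's own rates, two-sided testing, and usable data in both periods for the stated number of patients. It is a correction to the power statement and to its agreement with the analysis, not a finding of underpowering.

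**What to change.** Rewrite section 2.7 for a paired comparison, naming the test, the sidedness and the assumed overlap. Suggested text:

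*With usable data in both periods, 150 patients give at least 96% power (exact McNemar test, two-sided 5%) for 5% by day vs 20% by night over the whole feasible range of within-patient overlap, and about 97.5% if day and night status are independent. With 100 complete pairs, power is about 84% with no overlap and 88% under independence. At 80% power, 150 pairs detect 5% vs roughly 13-16%, for overlap from none to a within-patient correlation (phi) of 0.3.*

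Name the same paired test in section 2.11 for the day/night comparison of the proportion of patients with an episode, and say how patients with data in only one period are handled. The cost is one paragraph in section 2.7 and a line or two in section 2.11. Enrolment and data collection need not change.

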2.8 Recruitment

The trauma bay at Rigshospitalet will be equipped with the oximetry equipment, and measurement can be started as early as possible. At the trauma bay, a doctor will conduct the screening and inclusion of patients to the study at their arrival. After study inclusion, monitoring equipment will be attached by a nurse in the trauma bay. Subsequently a member of the study investigator group will obtain consent.

2.9 Data collection methods

Continuous pulse oximetry will be used to measure SpO_2 . SpO_2 , heart rate, pulse amplitude and alarm status will be measured every second during a 24-hour period on all study participants.

The Nellcor™ Portable SpO_2 Patient Monitoring System, PM10N (Medtronic, [name]) is used as monitoring device. The Covidien Nellcor FLEXMAX or a similar probe will be placed on the patients' index finger, alternatively another finger or toe. If there are no available extremities the patient will be excluded from the study.

If a patient has a peripheral venous catheter or a blood pressure cuff, the probe is placed on the other arm. The probe cable will be fastened with adhesive band across the back of the patient's hand, as an attempt to prevent untimely probe removal. The monitoring device will be placed in a telemetry bag with a soft fabric string which can be placed in the bed or around the patient's neck if awake. The data will be transferred and stored locally on a secure drive.

Since the study is observational, and we would like to identify episodes of hypoxemia that would go undetected under standard care, the alarm system on our monitoring device will be set restrictive. Alarm if $\text{SpO}_2 < 80\%$ or the heart rate is < 40 beats per minute or > 140 beats pr. minute.

Data collection will continue for up to 24 hours. If there is an untimely removal of the probe, the device will switch off, and data collection will stop at this point, unless the device is turned on again. After 24 hours of measurement, an investigator will collect the device and transfer the data by USB cable to a computer for secure storage and further analysis.

The following data will be obtained by accessing the study participants' medical records.

- Patient characteristics including name, unique patient identifier (civil registration number “CPR nummer”), age, sex, height and weight
- Pre-hospital circumstances including vital signs, Glasgow Coma Score (GCS), mechanism of injury, variables regarding airway management and oxygen treatment, use of sedatives and opioids, transportation mode to the trauma centre
- Vital signs at trauma centre arrival
- Clinical parameters during admission including vital signs, variables regarding airway management and oxygen treatment and use of sedatives and opioids
- Time points including date and time of trauma, trauma centre/ICU/ward/operating theatre/recovery room arrival and departure, time and duration of anaesthesia and surgery within first 24 hours
- Injury severity score (ISS) and abbreviated injury scale (AIS) scores
- Co-morbidities prior to trauma: Categorised in heart disease, lung disease and other diseases
- Hospital and ICU LOS
- Ischaemic events (myocardial infarction or cerebral ischemia)
- Specifics of possible brain injury (type and extent) and other cerebral complications
- 30-day mortality
- Active smoker (yes/no)

Patient data will be used to describe the population of study participants. This is of great importance, to make the results transferable to the relevant trauma patients.

Time points will be used to specify study participants' location at times of desaturation.

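### Outcomes are occurrence and absolute minutes with no denominator of monitored time, so shorter recordings and shorter department stays look healthier

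*Combined protocol and SAP*

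**What the plan says.** Section 2.9 (Data collection methods) sets the length of recording: "Data collection will continue for up to 24 hours". On loss of the sensor it says: "If there is an untimely removal of the probe, the device will switch off, and data collection will stop at this point". The sentence goes on to make an exception where the device is switched on again, so a removal may leave a gap or may end the recording. The same section has the cable taped to the hand to make early removal less likely.

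Section 2.5 (Outcomes) gives the primary outcome as "The occurrence and daily distribution of clinically relevant hypoxemic episodes defined as" SpO₂ below 90% for more than 5 minutes. The secondary outcomes are occurrence by department, occurrence of episodes longer than 30 minutes, and "Cumulated time of hypoxaemia" below 90%. None is expressed per hour or as a share of monitored time.

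Section 2.7 (Sample size) plans on shares of patients: "We estimate that 5% of patients during the day and 20% of patients during the night will experience hypoxemia". On failed recordings it says only that "it is expected that 10% will be excluded due to unsuccessful data collection", and it does not define unsuccessful.

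Section 2.11 (Statistics) lists an artefact definition, descriptive summaries, a t-test or Mann-Whitney test for day against night, a Kruskal-Wallis test for departments, and modified Wald intervals. It has no offset, rate, percentage of monitored time, or rule for partial recordings. Arrival and departure times for each department are collected (section 2.9), with the stated use of locating the patient at each desaturation.

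**The concern.** An episode can be seen only while the probe is on. A patient recorded for 6 hours has less opportunity to show an episode than one recorded for 24, and fewer minutes in which to accumulate hypoxaemia. If the outcome is a plain yes/no or a total of minutes, less recording reads as less hypoxaemia.

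Two comparisons are exposed. Stays in the trauma centre, theatre, recovery room, ICU and ward are unlikely to be of equal length, so occurrence by department mixes risk with length of stay even when every recording is complete. Day and night are clock windows, while recording starts on arrival. A complete 24-hour recording gives 12 hours in each window whatever the arrival time, but loss that builds up from arrival falls more heavily on whichever window comes later. The primary comparison is then partly a comparison of recording hours.

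**Working it through.** **The plan's own figure.** Inputs from section 2.7: 5% by day, 20% by night, alpha 5%, power 80%. The two-sided, pooled, two-group formula is n = [1.96·√(2·0.125·0.875) + 0.842·√(0.05·0.95 + 0.20·0.80)]² / 0.15² = 75.12 per group. Doubled, that is 150 (152 if each group is rounded up to 76). Adding 10% gives 150 × 1.10 = 165. The calculation uses one risk per window, which treats each window as fully observed.

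**Effect of recorded hours on occurrence.** Assume a constant hazard fitted to the plan's rates. Night: −ln(0.80)/12 = 0.0186 per hour. Day: −ln(0.95)/12 = 0.0043 per hour. The chance of at least one episode in h recorded hours is p(h) = 1 − (1 − p₁₂)^(h/12).

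| Hours recorded | Night share | Day share |
|---|---|---|
| 12 | 20.0% | 5.0% |
| 10 | 17.0% | 4.2% |
| 8 | 13.8% | 3.4% |
| 6 | 10.6% | 2.5% |
| 4 | 7.2% | 1.7% |

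The hourly rate ratio, 0.0186/0.0043 = 4.35 before rounding, is the same in every row.

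**Departments.** Suppose two departments share the hazard of 0.0186 per hour, with stays of 2 and 12 hours (assumed). The shares with an episode are 1 − 0.8^(2/12) = 3.7% and 20%, although the risk per hour is identical.

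**Cumulated time.** A patient below 90% for 3% of the time (assumed) shows 0.03 × 24 × 60 = 43 minutes over 24 hours, 22 over 12 hours and 11 over 6 hours. As a percentage, all three are 3%.

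**Day against night.** The documents give no distribution of recorded hours, so the size has to be assumed. Take exponential probe loss, with a share L lost by 24 hours and no restarts: λ = −ln(1 − L)/24. Mean hours in a window are the integral of exp(−λt) over those t in 0-24 that fall in the window, averaged over uniform arrival times. With L = 40%, λ = 0.0213 and total mean time is 0.40/λ = 18.79 hours.

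| Arrivals | Day h | Night h | Day share | Night share | Ratio |
|---|---|---|---|---|---|
| Full recording | 12 | 12 | 5.0% | 20.0% | 4.0 |
| 08-16 | 9.85 | 8.94 | 4.1% | 15.3% | 3.7 |
| 16-24 | 8.60 | 10.19 | 3.6% | 17.3% | 4.8 |
| Uniform over 24 h | 9.40 | 9.40 | 3.9% | 16.0% | 4.1 |

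Shares are p(h) at the mean hours. With L = 10%, the hours are 11.49 and 11.29 (arrivals 08-16) or 11.19 and 11.59 (arrivals 16-24). With L = 20%, they are 10.97 and 10.54, or 10.36 and 11.15.

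**False signal with no true difference.** Set 20% per 12 hours in both windows, 75 per group as in the plan's formula, and L = 40%. The chance that the test declares the shorter window healthier is 4.2% (arrivals 08-16) or 6.1% (arrivals 16-24), against 2.5% in that direction with equal hours.

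**The case against.** The strongest reply is that this is silence, not a stated bad method. That stands. A reader might infer that the plan prescribes a raw analysis in which a patient whose probe comes off counts as free of later hypoxaemia. No section says so. Section 1.2 speaks of incidences, and a t-test or Mann-Whitney test could be run on rates or percentages. What the documents do support is that the outcomes as worded carry no denominator and that nothing in section 2.11 supplies one.

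A reader might also infer that probe removal always ends the recording, or that the 10% in section 2.7 is a rule for dropping partial recordings. Neither follows. The device may be switched on again, and the 10% is a sample-size allowance with no definition of failure.

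On size, one can set 3 recorded night hours (5.4%) against a full day (5%) and conclude that the hypothesised difference could disappear. That needs a typical patient to have a complete day and a quarter of the night, and nothing in the documents suggests it. Under 40% loss the ratio moves from 4.0 to 3.7 or 4.8. Section 3.9 plans inclusion round the clock, so arrivals need not cluster in one window, though the arrival mix is not documented. That section promises a comparison of demographic data between day and night but does not mention monitored hours.

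Finally, replacing the primary analysis with a count model would change its target from the share of patients, on which the 150 rests, to an episode rate. That objection is sound, and the fix respects it.

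**Conclusion.** The point holds as a specification gap that is cheap to close. As written, episode occurrence and cumulated minutes are lower wherever less time is recorded. This is clearest for cumulated time and for the department comparison, where it needs only unequal stays and no probe loss.

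For the primary day-night comparison the effect is conditional. Under an assumed 40% loss by 24 hours and a constant hazard, the windows differ by about 0.9 hours (9.85 − 8.94) or 1.6 hours (10.19 − 8.60). The direction reverses with arrival time, and the imbalance is nil for uniform arrivals. Smaller losses give smaller differences. The documents do not support saying that the primary result is invalid, or that the effect would vanish. If loss is equal in both windows, the main cost is lower shares and less power. All of this assumes that hypoxaemia risk does not depend on whether the probe is on. If probe loss follows the patient's state, the bias could be larger or smaller than shown.

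**What to change.** In sections 2.5 and 2.11:

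- Report cumulated hypoxaemia as a percentage of artefact-free monitored time.
- Keep the share of patients with an episode, and report beside it episodes per monitored hour by period and department. As a supporting analysis, these could come from a Poisson or negative binomial model clustered on patient, with log monitored hours as offset.
- Include every patient with usable recording, stating what counts as usable and as unsuccessful. Add a sensitivity analysis in patients monitored through both full 12-hour windows.
- Tabulate monitored hours by day, night and department.

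The one-second data and the department times already hold the denominators, so the cost is wording and modest programming. There are two limits. Day events will be few for a count model: 5% of 150 is 7.5, so about 7 or 8 patients. And a rate reduces but does not remove bias if probe loss depends on the patient's state.
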